8.2 T-cell specific correlative science

Immunologic assessments will be performed prior to each cycle of therapy, and at 1, 3, and 6 months following the last cycle of therapy. At each time point, PBMC will be isolated from peripheral blood by ficoll density centrifugation and cryopreserved. Following completion of the study, PBMC will be thawed and 1 x 10⁶ PBMC will be cultured with lysate generated by freeze thaw cycle of 1 x10⁵ unselected MM cells. As a control, PBMC will be cultured with tetanus toxoid (10 ug/ml) or media alone. Following 5 days of coculture, expression of IFN- γ by CD4(+) and CD8(+) populations will be determined by intracellular FACS analysis. Cells will be restimulated with tumor lysate for 6 h and cultured overnight with 1 ug/ml GolgiStop. The cells will be stained with CD4 or CD8 antibodies conjugated to FITC and permeabilized with Cytofix/Cytoperm plusTM. Cells will be stained with PE-conjugated anti-human IFN- \square , fixed in 2% paraformaldehyde and analyzed by flow cytometry. The effect of therapy on levels of circulating tumor reactive T cells will be determined by quantifying IFN- \square expressing CD4(+) and CD8(+) T cells. The impact of CT-011 and len on tumor reactive T cells will be determined by comparing the pre-treatment levels with the peak level observed following therapy. The cytolytic capacity of tumor reactive lymphocytes will be determined by measuring expression of granzyme B and perforin in CD8(+) T cells following *ex vivo* exposure to autologous tumor lysate. The presence of naïve, memory effector, and central memory cells in the tumor reactive population will be determined by multichannel FACS analysis. The percentage of activated effector cells will be elucidated by quantifying the percentage of CD4(+)CD25(+) CD69(+) cells. Tregs will be quantified by assessing expression of FOXP3 for the CD4(+)CD25(+)CD127^{low/absent} population. When cell yields allow, we will assess the capacity of T cells to lyse autologous tumor cells in a standard chromium release assay. We will also examine the effect of CT-011 and len on immunologic responses against previously identified tumor antigens. XBP-1, OFD-1, SOX2, MUC1, and CD138 have been identified as MM associated antigens. In HLA-A2.1 patients, we will quantify the number of CD8(+) T cells binding tetramer constructed from these antigens (as cell yields allow) at serial time points in the circulation. The persistence of tetramer(+) cells in the circulation will be determined. Functional characteristics of the tetramer positive population will be determined by measuring IFN- γ , granzyme B, IL-4, and IL-10 expression in the tetramer(+) cells by intracellular FACS staining.

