4.4 Duration of Treatment

Patient can continue study treatment at the treating physician's discretion. Patients achieving at least a stable disease can continue treatment until one of the following is reached:

- Progression of disease
- Death
- Unacceptable toxicity
- Patient decision
- Treatment delay greater than 4 weeks.

Overall response will be assessed after 4, 8, and 12 cycles. If disease progression is observed at the end of Cycle 4 evaluation, all study therapy will be discontinued. In addition, study therapy will be discontinued at the time of disease progression as noted above. Otherwise patient can continue treatment until one of the above endpoints is reached.

Following the 30-day post-treatment follow-up assessment, additional evaluations will occur once per month (unless subject discontinued due to progression) until the earliest of the following events:

- Disease progression,
- The time of initiation of new therapy,
- Death or study completion.

Study completion is defined as 30 days after the last subject remaining on study medication discontinues study medication.

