5.8.5 Schedule for correlative studies

Laboratory correlative studies will be obtained at screening, days 3, 4, 6, 10 and 17 of cycle 1, days 3 of subsequent cycles and off study. Off-study correlates should be obtained at the time the patient is removed from protocol for any reason. In addition, continued T-cell correlate will be done at 1,3, and 6 months after removal from study. Specimens obtained include BM aspirate (10-15 ml in green-top tubes using heparinized syringe) and peripheral blood (Three-10 ml green top tubes, 2 for cells and 1 for plasma).

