5.8.6 Schedule of Events^a

Investigations	Screening	C1D3	C1D4	C1D6	C1D10	C1D17	C2D3	C3D3	C5D3	CxD3	End of Tx ^b	Follow Up ^p
History, physical examination, concomitant medication review	X	X					X	X		X	X	
Informed written consent	X											
Confirmation of disease relapse and prior treatment	X											
Skeletal survey (CT or MRI as clinically indicated) ^c	X										X	
MUGA or ECHO	X											
β-hCG ^d	X	X										
Toxicity evaluation	X	X					X	X		X	X	X
CBC / differential / platelets ^e	X	X					X	X	X	X ^f	X	
PTT, INR, TSH ^e	X											
BMP, glucose, magnesium ^e	X	X					X	X		X		
LFTs	X	X					X	X		X		
Beta 2 microglobulin ^g	X							X			X	
12-lead ECG ^h	X							X				
Serum monoclonal protein assessments ⁱ	X	X ⁱ					X ⁱ	X ⁱ		X ⁱ	X ⁱ	
24hr urine for creatinine clearance	X											
24hr urine monoclonal protein and immunofixation ^j	X	X ^j					X ^j	X ^j		X ^j	X ^j	
BM biopsy, unilateral ^k	X								X ^k		X ^k	
CT-011 Given		X					X	X	X	X		
Prescribe lenalidomide via RevAssist ^l	X											
T-cell, NK-cell, and CD14 Correlative studies ^m	X	X	X	X	X	X	X	X	X	X	X	X

CT-011 PK ⁿ		X	X	X	X	X	X				
ADA (immunogenicity) ^o	X										

- a. With the exception of PK samples, all other time points have a +/- 4 day window to accommodate weekends, holidays, and for patient convenience.
- b. Off study correlates will be done. In addition, continued T-cell correlate will be done at 1,3, and 6 months after removal from study
- c. Skeletal survey will be done at baseline and may be done at evidence of progression of disease. CT scan will be done to document size of plasmacytoma if this is the only measurable disease.
- d. Female patients of childbearing potential (FCBP, defined in section 8.5) must have a negative pregnancy test (β -hCG) as required by the RevAssist program. Lenalidomide and dexamethasone will start on day 1 of each cycle. Patients do not need to be in clinic to initiate this as all patients would have been exposed to both. Lenalidomide will be ordered for the next cycle. A pregnancy test (urine or serum β -HCG) will also be ordered at this time. Patients must have a negative β -HCG result prior to starting lenalidomide on day 1 of each cycle.

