- e. CBC d/p will be monitored biweekly in cycles 1 to 4, then monthly thereafter. Chemistry tests, including electrolytes, glucose and serum creatinine, should be performed every 2 weeks during the first 2 months of therapy and once a month thereafter. Serum electrolyte monitoring should include potassium, magnesium and calcium. PTT, INR and TSH will be checked every 2 months.
- f. CBC/d/p should also be checked on day 17 of a cycle where lenalidomide's dose has been escalated.
- g. Beta 2 microglobulin will be done after every 2 cycles and at evidence of progression of disease.
- h. Baseline and periodic ECGs should be performed during treatment as indicated in the flow chart. In patients who have ECG abnormalities, ECGs should be performed more routinely as clinically indicated. ECGs post-baseline should be performed as indicated
- i. Myeloma monoclonal protein assessments (Serum protein electrophoresis & immunofixation, immunoglobulin levels, serum free light chain assay) will be performed on day 3 of each cycle (when patients come in for CT-011 infusion) as well as off study.
- j. 24hr urine monoclonal protein assessment (Urine protein electrophoresis & immunofixation) will be performed at screening and as required for response assessment.
- k. Unilateral bone marrow (BM) biopsy will be done at baseline and at end of 4th cycle and evidence of progression for patients with non secretory multiple myeloma
- l. Lenalidomide must be prescribed through and in compliance with Celgene's RevAssist® program. Prescriptions must be filled within 7 days. Any unused lenalidomide should be returned to the patient for disposition in accordance with the RevAssist® program.
- m. T-cell, NK-cell, and CD14 correlates will be collected prior to CT-011 dosing on C1D3, C1D4, C1D6, C1D10, C1D17 and then on Day 3 of all subsequent cycles. T-cell correlates only will also be collected at 1, 3, and 6 months after discontinuation of protocol therapy.
- n. Samples for CT-011 PK determination will be collected in cycle 1 prior to CT-011 infusion, immediately at the end of the infusion, 1 hour after end of infusion, approximately 24(C1D4), 72(C1D6), 168 (C1D10) & 336 (C1D17) hrs – and just prior to next (cycle 2) infusion. Off-study correlates should be obtained at the time the patient is removed from protocol for any reason.

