Correlative analyses will also be done, including analysis of markers of the immunogenicity of CT-011. In particular, we will evaluate biological and cellular markers in patients treated with CT-011, measure PD-L1 expression on MM cells, percentage increase in NK cell activity, migration, immune complex formation, and cytotoxicity. Other markers such as plasma cell IHC baseline expression to characterize immunologic markers of MM cells that are responsive to CT-011 such as TNF-alpha, IFN-gamma, CD4, CD8, and granzyme B will be evaluated in addition to markers of MM cells responsive to lenalidomide (Spars, IRF-4). Changes in these markers before and after therapy will be explored using graphical analyses as well as summarized quantitatively. We will also explore how changes in these correlative markers may differ based on whether or not the patient achieved a response or not; to accomplish this, we will utilize different plotting characters and colors for successes vs. not in the graphical analyses to help identify potential patterns, and summarize the changes quantitatively between successes vs. not. Given the total sample size available, we expect

that these analyses will be exploratory at best, but will provide important insights into mechanisms of action and vital preliminary data for future studies and hypothesis generation.

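### Section 8.2 judges the T-cell effect by one baseline against the peak of several later samples, a summary that rises even when treatment does nothing

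*Combined protocol and SAP*

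**What the plan says.** Section 8.2 takes T-cell samples "prior to each cycle of therapy, and at 1, 3, and 6 months following the last cycle of therapy". It then determines the impact of the two drugs on tumor-reactive T cells by "comparing the pre-treatment levels with the peak level observed following therapy". It states no window for the peak, no fixed visit, no common number of samples and no untreated comparison group.

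Section 5.8.5 has a denser schedule: correlative samples "will be obtained at screening, days 3, 4, 6, 10 and 17 of cycle 1, days 3 of subsequent cycles and off study", with further T-cell samples 1, 3 and 6 months after removal from study. In section 5.8.6, footnote m says these "correlates will be collected prior to CT-011 dosing on C1D3", and footnote d says "Lenalidomide and dexamethasone will start on day 1 of each cycle". The cycle 1 day 3 sample therefore precedes CT-011 but follows lenalidomide. Only the screening sample precedes both.

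Time on treatment depends on outcome. Section 4.4 says "If disease progression is observed at the end of Cycle 4 evaluation, all study therapy will be discontinued", while section 4.3 keeps responders and patients with stable disease on treatment for at least eight more cycles.

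Section 6.1.2 plans plots and summaries of marker change before and after therapy, and will "summarize the changes quantitatively between successes vs. not". It calls these analyses exploratory and names no test. It does not mention the peak, and its marker list does not name the tumor-lysate assay of section 8.2.

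**The concern.** A maximum is chosen because it is high. Setting it against one unselected baseline value shows a rise in most patients even if nothing has changed. If the peak is sought over every later sample, patients who stay on study longer have more chances at a high value and so a larger apparent rise.

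This matters in two places. Section 2.4 lists immunomonitoring of T and NK cells and ex-vivo immune function as a secondary endpoint. Section 6.1.2 lets correlative outcomes help decide whether the regimen is promising when 10 or 11 of the 29 evaluable patients respond. A marker that nearly always appears to rise would push that judgement in one direction.

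**Working it through.** The documents give no figure for the T-cell comparison, so there is none to reproduce. The design figures in section 6.1.2 do reproduce. With n=29 and cut-offs of 9 and 12, the binomial gives type I error 0.039, type II error 0.031, eta 0.834 and pi 0.868, against the stated 4%, 3%, 0.83 and 0.87. The chance of landing on 10 or 11 responses is then 1 − 0.834 − 0.039 = 0.127 at a true rate of 25%, and 1 − 0.031 − 0.868 = 0.101 at 50%.

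**Number of later samples, k**

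- Post-treatment samples only (months 1, 3, 6): k = 3.
- All later samples under section 8.2: k = (cycles − 1) + 3. Stopping after cycle 4 gives 3 + 3 = 6; 12 cycles give 11 + 3 = 14.
- All later samples under section 5.8.5, counting only those after CT-011 starts (4 in cycle 1, one per later cycle, 1 off study, 3 follow-up): 4 + 3 + 1 + 3 = 11 after 4 cycles, and 4 + 11 + 1 + 3 = 19 after 12.

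**Expected result with no treatment effect**

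If a patient's k+1 values are exchangeable and continuous, each is equally likely to be the largest, so P(peak > baseline) = k/(k+1). For independent normal noise, the expected peak minus baseline is the expected maximum of k standard normals, E(k) = ∫ x·k·φ(x)·Φ(x)^(k−1) dx, in within-patient SDs. The last two columns are simulated with first-order autoregressive correlation of 0.8 between successive samples.

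| Samples searched | k | Rise, independent (SD) | Patients above baseline | Rise, correlation 0.8 (SD) | Patients above baseline |
|---|---|---|---|---|---|
| Months 1, 3, 6 only | 3 | 0.85 | 75% | 0.42 | 70% |
| 8.2, 4 cycles | 6 | 1.27 | 86% | 0.76 | 80% |
| 8.2, 12 cycles | 14 | 1.70 | 93% | 1.22 | 90% |
| 5.8.5, 4 cycles | 11 | 1.59 | 92% | not run | not run |
| 5.8.5, 12 cycles | 19 | 1.84 | 95% | not run | not run |

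**What this means as a fold change**

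The within-patient CV is not in the documents. With s = √ln(1 + CV²), the false fold rise on the log scale is exp(s·E(k)) under independent noise:

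- assumed CV 20%: 1.29 at k=6 and 1.40 at k=14;
- assumed CV 30%: 1.45 and 1.65;
- assumed CV 50%: 1.82 and 2.24.

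**If the peak change were compared by response**

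This assumes the all-later-samples reading of section 8.2, no effect, independent noise, and 12 responders all at k=14 against 17 non-responders.

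- All 17 at k=6: gap 1.70 − 1.27 = about 0.43 SD (0.43 to 0.49 for correlations of 0, 0.5 and 0.8).
- 8 of the 17 stable and also at k=14: non-responder mean (8×1.703 + 9×1.267)/17 = 1.472, gap 0.23 SD.
- 8 of the 17 stopping after cycle 2 (k=4, E=1.029): mean (8×1.029 + 9×1.267)/17 = 1.155, gap 0.55 SD.
- Peak over months 1, 3 and 6 only: k=3 for all, so no gap from sample count.

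**A fixed visit, or the mean of the later samples**

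Under the same no-effect simulation, the average change is 0.00 SD and about 50% of patients rise.

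**The case against.** The strongest reply is that these analyses are exploratory and carry no test or alpha. That is true, and it rules out one tempting inference: that the plan has a false-positive rate near 100%. A paired t-test at 5% on the peak change in 29 patients would be falsely significant in 83% to 94% of trials at k=3 and in over 99% at k=6 or 14. But the plan specifies no such test, so those rates are only illustrative. The bias does not need a test. It sits in the descriptive summary.

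A reader might also infer that the planned responder comparison is biased by time on study. The documents do not establish that. Section 6.1.2 does not say that it uses the peak. The dependence on time on study needs the all-later-samples reading; if the peak means only the three post-treatment samples, k is 3 for everyone. Stable non-responders stay on treatment as responders do, so any assumed split of k is one scenario among several.

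Sections 8.2 and 5.8.4 do contain safeguards: tetanus toxoid and media-alone cultures, and thawing a patient's samples together where possible. These control the assay and reduce batch variation. They do not offset the selection of a maximum.

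**Conclusion.** The peak-versus-baseline rule in section 8.2 is biased upward and should not be the main T-cell summary. With no effect, the false rise is 0.85 to 1.70 within-patient SD for k from 3 to 14 under independent noise, and about 0.42 to 1.22 SD with serial correlation of 0.8. The size rests on an SD and a correlation that the documents do not give. The direction holds whenever there is any within-patient variation and k exceeds 1.

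Growth of the bias with time on study is conditional on taking the peak over all later samples. Bias in the responder comparison is conditional on that and on section 6.1.2 using the peak change. Neither should be stated as what the plan does.

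The response-rate classification at 9 or fewer, or 12 or more, responses is unaffected. The practical risk lies in the secondary immune endpoint and in the judgement made at 10 or 11 responses.

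**What to change.** In section 8.2, replace the peak with the log-scale change from the screening sample to one pre-specified early visit that nearly all patients reach before outcome-driven discontinuation or added dexamethasone. The pre-CT-011 sample on day 3 of cycle 2 is a candidate. A repeated-measures model of all samples by visit is the alternative. Use the same visit for any responder versus non-responder summary, and say so in section 6.1.2. Keep the peak as description only, with a stated window and an equal number of samples per patient.

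Day 3 of cycle 5, or a mean over cycles 2 to 5, would be a poor main measure. Patients who progress at the end of cycle 4 have no cycle 5 sample, and dexamethasone may by then have been added for stable disease, so exposure differs by response. The documents disagree on when dexamethasone can start: after 3 cycles in section 5.3, after 2 in section 6.1.2, after cycle 1-2 in one sentence of section 4.3, and day 1 of each cycle in footnote d of section 5.8.6. Those passages must be reconciled before the visit is fixed. The sampling times in sections 8.2 and 5.8.5 should be aligned as well.

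The cost is wording only; no new samples are needed. The downside is that an early fixed visit may miss a later or transient rise, which the model by visit and the descriptive peak would still show.

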
8.3 NK-cell specific correlative science

We will quantitate CD56^{bright} and CD56^{dim} NK cell subsets in PBMC and other markers of NK cell maturity (proportion of NK cells expressing CD16 and CD117) and developing intermediates in peripheral blood. Preliminary data from another group suggest that CT-011 upregulates activation markers on NK cells in an *in vitro* system.⁵⁸ We will also perform immunophenotyping of NK cell subsets for expression of trafficking antigens (in particular CXCR4 which we have shown to be modulated by CT-011 on NK cells) and markers of activation (CD158, CD69) and degranulation (LAMP-1, LAMP-3, CD107a, CD107b, CD159, and CD314) which may be influenced by CT-011 and len. Notably, our group has optimized an “immunome” flow cytometry-based profiling technique to allow these characterizations from a very modest amount of pt PBMC to minimize volume of blood collected for correlative science studies. Finally, we will perform *ex vivo* functional assays against MM cell line targets and purified, autologous MM tumor samples obtained at baseline and after each cycle of therapy including trafficking, immune complex and cytotoxicity assays as described by our group previously.⁵⁹ We will also attempt to verify our preclinical finding regarding down modulation of PD-L1 on MM tumor cells by len by comparing PD-L1 expression on pt MM tumor cells at baseline and after one cycle of therapy. We will purify CD138(+) MM cells from bone marrow aspirates of pts obtained at baseline and after one cycle of treatment and assess PD-L1 expression by flow cytometry.

8.4 CD14(+) monocyte specific, correlative science

We will evaluate the expression of PD-L1 and PD-L2 on CD14(+) monocytes at baseline and after treatment with CT-011 after each cycle of therapy. We will specifically study the induction of these antigens on CD14(+) cells as a consequence of CT-011 administration. We will attempt to correlate the expression PD-L1 on CD14(+) cells with clinical activity determined by response rate and progression-free survival if allowable by sample size power. Otherwise, we will limit these analyses to hypothesis-generating, descriptive evaluation.

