4 STUDY DESIGN AND DURATION

4.1 Study Design

This is a non-randomized open-label phase I/II study for patients with relapsed and refractory multiple myeloma. For the phase I part, we will conduct a standard 3+3 design over 4 main dose levels cohorts evaluating 1.5, 3, 3, and 6 mg/kg of CT-011 given intravenously every 4 weeks (every 28 days) on day 3, and lenalidomide given at 15, 15, 25, and 25 mg orally daily on days 1-21 of a 28-day cycle, to determine the maximum tolerated dose. The phase II will commence once the MTD is determined, and this dose level combination for CT-011 and lenalidomide will be used for the phase II portion of this trial. Patients will be assessed for response at the end of cycle 4 or sooner if necessary according to the IMWG response criteria.

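### Sections 8.3 and 8.4 credit marker changes seen after a cycle of both drugs to one drug alone; they should be reported as combination effects, with only a short early blood contrast around the first CT-011 infusion

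*Combined protocol and SAP*

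**What the plan says.** Treatment: section 4.1 has "lenalidomide given at 15, 15, 25, and 25 mg orally daily on days 1-21 of a 28-day cycle", and section 5.1.3 gives CT-011 on day 3 of each cycle. Section 2.1 describes a single-arm study.

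Monocytes (8.4): "We will evaluate the expression of PD-L1 and PD-L2 on CD14(+) monocytes at baseline and after treatment with CT-011 after each cycle of therapy". The next sentence gives the interpretation: "We will specifically study the induction of these antigens on CD14(+) cells as a consequence of CT-011 administration".

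Tumour cells (8.3): the aim is to verify "down modulation of PD-L1 on MM tumor cells by len by comparing PD-L1 expression on pt MM tumor cells at baseline and after one cycle". The material is marrow: "We will purify CD138(+) MM cells from bone marrow aspirates of pts obtained at baseline and after one cycle of treatment".

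Sampling: Schedule of Events note m says "T-cell, NK-cell, and CD14 correlates will be collected prior to CT-011 dosing on C1D3", and lists C1D4, C1D6, C1D10, C1D17 and day 3 of later cycles. For marrow, note k says "Unilateral bone marrow (BM) biopsy will be done at baseline and at end of 4th cycle" and goes on to add progression and to mention non-secretory disease. Section 5.8.5 lists marrow aspirate among the correlative specimens without tying it to particular visits.

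Analysis: section 6.1.2 plans graphical and quantitative description of marker changes from before to after therapy and calls this work exploratory. It names no reference sample, and no section defines baseline for the correlates.

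**The concern.** The same two-drug exposure is read as a CT-011 effect in 8.4 and as a lenalidomide effect in 8.3, and PD-L1 is measured in both. Section 8.3 expects lenalidomide to move PD-L1 on tumour cells, so 8.4 has no ground for treating lenalidomide as neutral for PD-L1 on monocytes. A lenalidomide effect could be reported as CT-011 pharmacodynamics, or the reverse. Section 6.1.2 intends these data to inform mechanism and to seed later studies, so a wrong label would carry forward.

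Later cycles add more. Section 5.2.1 lets lenalidomide rise by 5 mg per cycle from cycle 2, and section 5.3 lets dexamethasone be added after 3 cycles. Section 1.5 recognises that steroids can affect NK-cell activity.

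**Working it through.** The plan gives no figure to reproduce here. The check counts drug exposure at each scheduled sample.

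**Inputs.** Lenalidomide days 1-21 of 28 (4.1); CT-011 on day 3 (5.1.3); sample days (5.8.5 and note m); a window of 4 days either side for non-PK time points (note a); CT-011 half-life 270 to 410 hours (1.4.2).

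**Lenalidomide doses before a sample.** On cycle 1 day d (d up to 21) this is d - 1 if that day's dose has not been taken, and d if it has. For C2D3 it is 21 + 2 = 23, or 21 + 3 = 24.

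| Sample | Lenalidomide doses | CT-011 infusions | Doses added since C1D3 |
|---|---|---|---|
| C1D3, pre-infusion | 2 or 3 | 0 | - |
| C1D4 | 3 or 4 | 1 | 1 |
| C1D6 | 5 or 6 | 1 | 3 |
| C1D10 | 9 or 10 | 1 | 7 |
| C1D17 | 16 or 17 | 1 | 14 |
| End of cycle 1 | 21 | 1 | 18 or 19 |
| C2D3, pre-infusion | 23 or 24 | 1 | 21 |

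**After-cycle contrasts.** From screening to the end of cycle 1, a patient on schedule gains 21 lenalidomide doses and one infusion. If the sample is C2D3, the gain is 23 or 24 doses and one infusion. No after-cycle sample reflects one drug.

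**Has CT-011 gone by then?** Assuming single-phase decay, the fraction left 28 days (672 hours) after infusion is 0.5^(672/270) = 0.18 to 0.5^(672/410) = 0.32. Washout therefore does not rescue the lenalidomide reading in 8.3.

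**What C1D3 offers.** It follows 2/21 = 10% to 3/21 = 14% of the cycle 1 lenalidomide doses. C1D3 to C1D4 adds one infusion and about one lenalidomide dose; C1D3 to C1D6 adds one infusion and about three. C1D10 and C1D17 add about 7 and 14 doses and so are combination contrasts again.

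**Timing.** The lead-in from day 1 to day 3 is 2 days, shorter than the 4-day allowance on either side. Read literally, a nominal C1D3 draw could fall anywhere from 3 - 4 = -1, before lenalidomide starts, to day 3 + 4 = 7. PK draws are exempt from the window, but note a does not extend the exemption to correlates taken on the same days.

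**Is screening free of lenalidomide?** Not necessarily. Section 3.1 accepts stable disease on lenalidomide and entry at any time after the last line. Section 5.8.1 allows screening assessments up to 4 weeks before treatment.

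**The case against.** The strongest reply is that these are secondary, descriptive analyses. Section 6.1.2 says they are exploratory, 8.3 promises only an attempt at verification, and 8.4 falls back to description if numbers are small. Section 2.4 sets the endpoint as CT-011 pharmacodynamics in combination with lenalidomide, which a combination readout satisfies. All this stands and sets the severity. It does not license a single-drug label on a two-drug change.

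A reader might infer more than the documents support, in four ways:

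- **That C1D3 would separate the drugs.** It would not. Few lenalidomide doses precede it, and lenalidomide continues alongside CT-011. No C1D3 marrow is marked in the Schedule of Events, so it cannot serve the tumour-cell assay.
- **That the plan has rejected C1D3 as reference.** Baseline is simply undefined for the correlates. For marrow and skeletal survey the schedule's baseline is the screening column, which makes screening the likelier reading, but this is inference.
- **That all correlates are misattributed.** Section 8.2 credits both drugs, and 8.3 says the NK markers may respond to both. Only two comparisons carry the single-drug wording.
- **That the after-one-cycle marrow is certainly unscheduled.** Note k concerns the clinical biopsy. Section 5.8.5 lists aspirate among specimens for a schedule that includes day 3 of later cycles, which could cover C2D3. The passages are unclear together, not plainly contradictory.

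The lead-in may also not be lenalidomide alone. Note d has dexamethasone starting with lenalidomide on day 1 of each cycle, and the synopsis describes phase II as including dexamethasone, whereas section 5.3 adds it only after 3 cycles. These passages must be reconciled.

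**Conclusion.** The point holds as a minor correction to exploratory analyses. Two comparisons assign to one drug a change that follows 21 planned lenalidomide doses and one CT-011 infusion, and a single-arm combination design cannot support that. The pre-infusion C1D3 blood sample allows a closer, still imperfect contrast over 1 to 3 days, with about 1 to 3 further lenalidomide doses mixed in.

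This rests on dosing as scheduled, on dexamethasone not starting before C1D3, and on draws close to their nominal days. The response-rate test, sample size and safety conclusions are unaffected, and the documents do not support reading this as failure of the pharmacodynamic endpoint.

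**What to change.** 1. In 8.3 and 8.4, describe every after-cycle change, including marrow PD-L1, as an effect of the combination. Treat the C1D10 and C1D17 blood changes the same way.
2. Define baseline for each correlate in 6.1.2 or section 8.
3. For blood markers, use pre-infusion C1D3 as reference for an early CT-011-added contrast limited to C1D4 and C1D6. State that it still includes about 1 to 3 lenalidomide doses.
4. Report screening to C1D3 only as an early on-lenalidomide change, noting that recent prior lenalidomide is possible.
5. Record and analyse actual dose and draw times.
6. Flag samples taken after dexamethasone starts or the lenalidomide dose changes.
7. Reconcile the after-one-cycle aspirate in 8.3 with 5.8.5 and note k, and reconcile the passages on when dexamethasone starts.

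The cost is wording plus capture of times. The blood samples are already scheduled. Any marrow cost depends on how item 7 is settled.
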